### 9.2 Source Documents

Source data is all information, original records of clinical findings, observations, or other activities in a clinical trial necessary for the reconstruction and evaluation of the trial. Source data are contained in source documents. Examples of these original documents, and data records include: hospital records, clinical and office charts, laboratory notes, memoranda, subjects' diaries or evaluation checklists, pharmacy dispensing records, recorded data from automated instruments, copies or transcriptions certified after verification as being accurate and complete, microfiches, photographic negatives, microfilm or magnetic media, x-rays, subject files, and records kept at the pharmacy, at the laboratories, and at medico-technical departments involved in the clinical trial.

### 9.3 Case Report Forms

The study case report form (CRF) is the primary data collection instrument for the study. All data requested on the CRF must be recorded. All missing data must be explained. If a space on the CRF is left blank because the procedure was not done or the question was not asked, write "N/D". If the item is not applicable to the individual case, write "N/A". All entries should be printed legibly in black ink. If any entry error has

been made, to correct such an error, draw a single straight line through the incorrect entry and enter the correct data above it. All such changes must be initialed and dated. DO NOT ERASE OR WHITE OUT ERRORS. For clarification of illegible or uncertain entries, print the clarification above the item, then initial and date it.

## 10.0 DATA SAFETY AND MONITORING BOARDS

The Albert Einstein College of Medicine/Albert Einstein Cancer Center Data Safety Monitoring Committee (DSMC) has the responsibility for ensuring data and safety monitoring along with the PI who is ultimately responsible for the ongoing monitoring and safety of clinical protocols. The primary functions of the AECC DSMC are as follows:

1. To review and ensure protocol compliance with dose escalation in phase I trials
2. To review/assure protocol compliance for all trials that have two-stage phase II designs,
3. Reviewing all internal and external serious adverse reports, investigator alerts, action letters, and other safety reports for trials being performed at AECC-affiliated institutions and;
4. To implement and to determine the adequacy of DSM plans of all approved protocols.

The DSMC is an independent committee and meets on a monthly basis. During its monthly meeting, the DSMC will review serious (grade 3 or higher) adverse events from this study. In the event that the DSMC decides that a revision is warranted, the committee will immediately notify the principal investigator of this study. The DSMC has the authority to close trials to patient accrual should the risk to patients be excessive or outweigh the potential benefits of the study. All study suspensions and closures will be forwarded to the IRB/CCI and study sponsor from the DSMC.

## 11.0 ADVERSE EVENTS

An adverse event (AE) is defined as any untoward medical occurrence in a patient or clinical investigation subject and does not necessarily have to have a causal relationship with study treatment. An AE can therefore be any unfavorable and unintended sign (including an abnormal laboratory finding), symptom, or disease temporally associated with the use of treatment. During clinical trials, AEs can be spontaneously reported or elicited during open-ended questioning, examination, or evaluation of a subject.

AEs will be recorded in the case report form for the duration of the trial, regardless of whether or not the event(s) are considered related to trial intervention or medication. All AEs considered related to trial intervention or medication will be followed until resolution, even if this occurs post-trial.

### 11.1 Adverse Event Definitions

Adverse Event (AE): any new, undesirable medical experience or change of an existing condition that occurs during or after treatment, whether or not considered product-related.

Serious Adverse Event (SAE): An AE occurring at any dose that results in any of the following outcomes (CFR 312.32)

Death

Life-threatening adverse experience

Inpatient hospitalization or prolongation of existing hospitalization excluding those for study therapy administration, transfusional support, disease staging/re-staging procedures, thoracentesis / paracentesis, or placement of an indwelling catheter, unless associated with other serious events

Persistent or significant disability or incapacity

Congenital anomaly / birth defect.

The definition of SAE also includes important medical event. Medical and scientific judgment should be exercised in deciding whether expedited reporting is appropriate in other situations, such as important medical events that may not be immediately life-threatening or result in death or hospitalization but may jeopardize the patient or may require intervention to prevent one of the other outcomes listed in the definition above. These should also usually be considered serious. Examples of such events are intensive

treatment in an emergency room or at home for allergic bronchospasm; blood dyscrasias or convulsions that do not result in hospitalization; or development of drug dependency or drug abuse. A new diagnosis of cancer during the course of treatment should be considered an important medical event.

The definition of “related” is that there is a reasonable possibility that the drug or the study intervention caused the adverse experience.

**Unexpected Adverse Event:** An AE that is not mentioned in the Investigator's Brochure or package insert or the specificity or severity of which is not consistent with the investigator's brochure or package insert.

**Life-threatening:** Any adverse experience that places the patient or subject, in the view of the investigator, at immediate risk of death from the reaction as it occurred. It does not include a reaction that, had it occurred in a more severe form, might have caused death.

AEs will use the descriptions and grading scales found in the revised Common Terminology Criteria for Adverse Events (CTCAE) version 4.0 (Appendix B). A list of AEs that have occurred or might occur can be found in sections above.

## 11.2 Adverse Event Reporting

Study site personnel must notify the PI and the sponsor immediately of any SAE experienced by a patient. In general, SAEs assessed as clearly being due to disease progression, and not due to study drug(s), should be excluded from AE reporting. Study-specific clinical outcomes of death because of disease progression are exempt from SAE reporting, unless the investigator deems them related to use of the study drug. Hospitalization for study drug administration is not an SAE.

The following steps will be taken to report promptly and document accurately any SAE, even if it may not appear to be related to the study treatment:

Report the SAE to the PI and the treating physician by email, telephone or fax within 24 hours of becoming aware that a patient has experienced an SAE.

Record the SAE accurately on the AE page of the patient's CRF.

Using the standard IRB-SAE report form, submit all known patient information within 24 hours of SAE occurrence to the clinical trial office to submit to IRB and DSMB. Date and sign each report before submission. Include the following

information (or as much as possible to obtain and still report the event within 24 hours):

- Study protocol number and indication
- Study site and investigator's identification
- Patient's ID (patient number and initials), age or date of birth, and sex
- Date of enrollment
- Description of SAE, including date of onset and duration, severity, and outcome
- Date of first and most recent (last) dose administered
- Action taken regarding study treatment
- Relationship of SAE to study treatment
- Concomitant medications, including regimen and indication
- Intervention, including concomitant medications used to treat SAE
- Pertinent laboratory data/diagnostic tests conducted and date
- Pertinent medical history of patient
- Date of hospital admission/discharge
- Date of death (if applicable)

Within 10 days of initial IRB notification, the PI is required to submit a completed Adverse Event Report to the IRB. The treating physicians should perform appropriate diagnostic tests and therapeutic measures and submit all follow-up substantiating data, such as diagnostic test reports and autopsy report to the PI, IRB, and DSMB.

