More recently, a prospective clinical trial reported on the effectiveness of SBRT for patients with MESCC, as measured by the reduction of epidural tumor volume and improvement in thecal sac patency. They enrolled 62 patients with MESCC who were treated with 14-20 Gy in a single fraction. The results demonstrated a 64% reduction of the epidural tumor volume at 2 months following treatment, with 80% of the patients also showing improvement in thecal sac patency. Notably, however, 16% of these patients had neurologic progression (9/62 patients). Of these 9 patients, 5 had decompressive surgery thereafter in which 2 showed necrosis, 2 died from intraoperative complications and 1 had tumor progression [12]. This trial indicated that a radiographic response can be observed rapidly, however there is clearly a risk of neurological toxicity from delivering single doses of 14 Gy or higher to tumors abutting the spinal cord.

Previous studies have estimated spinal cord constraints ranging from 10-14 Gy for single fraction SBRT treatments [10, 13, 14]. RTOG 0631, an ongoing prospective randomized trial which investigated the use of SBRT for palliation of spine metastases (16 Gy SBRT vs. 8 Gy x 1 conventional), applied these constraints using 10 Gy to 10% of the spinal cord (cross sectionally) to a maximum of 6mm above and below the target volume, and max dose of 14 Gy. However, patients are excluded if there was frank epidural compression within 3 mm of the spinal cord.

Based on the above findings, we are proposing a trial for patients with inoperable MESCC utilizing adaptive planning and a staged application of radiotherapy. Such an approach can potentially deliver therapeutic doses to the tumor while respecting the established spinal cord constraints. We hypothesize that a single fraction of treatment may induce a short-interval radiographic response (within approximately 2-3 weeks), which can then be used to plan an additional treatment if needed. The response may

also allow us to achieve therapeutic dose levels by reducing the volume of overlap with the spinal cord. We will also observe the radiographic response from high-dose single fraction regimens if decompression can be achieved in this fashion.

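### Section 11.2 both requires and excludes reporting of SAEs attributed to progression, so a serious neurologic event at the treated level can be left out of the reports to the DSMC

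*Combined protocol and SAP*

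**What the plan says.** Section 11.2 of the combined protocol and SAP gives these instructions in turn:

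- It opens with a general duty: "Study site personnel must notify the PI and the sponsor immediately of any SAE experienced by a patient".
- It then states, qualified by the words *in general*, that "SAEs assessed as clearly being due to disease progression, and not due to study drug(s), should be excluded from AE reporting".
- It adds an exemption for deaths, where the test is again one of relation to the drug (the last word is cut here): "Study-specific clinical outcomes of death because of disease progression are exempt from SAE reporting, unless the investigator deems them related to use of the study".
- The next paragraph sets out steps to "report promptly and document accurately any SAE, even if it may not appear to be related to the study treatment". They include an SAE form, due within 24 hours, that the clinical trial office passes to the IRB and the DSMB.

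Section 11.0 has a separate recording rule: "AEs will be recorded in the case report form for the duration of the trial, regardless of whether or not the event(s) are considered related". Section 11.1 counts lasting or significant disability as serious. It calls an event related when there is a reasonable possibility that the drug or the study intervention caused it.

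Section 10.0 says that at its monthly meeting "the DSMC will review serious (grade 3 or higher) adverse events from this study", and gives the committee power to close accrual. Section 4.4 lists grade 3 or higher toxicity as a secondary endpoint only where it is treatment-related.

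**The concern.** Excluding progression events from SAE reporting is workable when progression is easy to tell from harm by the treatment. Here the treated tumour lies against the organ at risk. Section 2.1 says untreated compression can end in paraplegia. Section 2.3 says large single doses to tumours touching the cord carry a risk of neurological toxicity. New weakness or loss of ambulation at the treated level could be either.

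The series cited in Section 2.3 shows the difficulty. Nine of its patients had neurologic progression, and of these "5 had decompressive surgery thereafter in which 2 showed necrosis, 2 died from intraoperative complications and 1 had tumor progression".

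At stake is whether the committee that can close accrual sees such events. One attribution decision can remove an event both from the SAE reports and from the grade 3 or higher endpoint. Section 11.2 does not say who decides that a non-fatal event is clearly progression, or on what evidence. Section 6.1 gives radiographic response to an attending outside the patient's care; attribution of adverse events has no similar provision.

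**Working it through.** The point rests on a comparison of text, followed by one illustration of scale.

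**One event under each rule.** Suppose a patient has serious new leg weakness at the treated level and it is attributed to progression. If it amounts to significant disability, it is an SAE under Section 11.1.

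| Rule | Result |
|---|---|
| 11.0, case report form | Recorded |
| 11.2, opening sentence | PI and sponsor notified |
| 11.2, progression exclusion | Left out of AE reporting |
| 11.2, reporting steps | Reported, with a form for the IRB and DSMB |

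The last two rows conflict, and nothing ranks them. If the exclusion is read as an exception to the general duty, the form is not sent. If the reporting steps govern, it is. Two sites could act in opposite ways and each point to the text.

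**The attribution test.** The exclusion needs two conditions: the event is clearly due to progression, and it is not due to study drug(s). Because the intervention is radiotherapy, the second condition as worded screens out almost nothing. Section 11.1 includes the study intervention in its definition of related; the exclusion and the death exemption in 11.2 do not.

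**Where the event would still appear.** It would be in the case report form (11.0), in the neurologic evaluations at day 14-21 and weeks 8-10 (4.2), and in the ambulation endpoint (4.4). Deaths and disease progression count in the survival endpoints (4.4). No text sends these data to the DSMC. The SAE form is the only route described from the site to the board for an individual event. (I take the DSMB of 11.2 and the DSMC of 10.0 to be the same body.)

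**Illustration of scale.** Inputs: 9 of 62 patients with neurologic progression, printed as 16% (2.3); 15 patients (Schema) or 24 (7.1).

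- Check of the printed rate: 9/62 = 14.5%, whereas 10/62 = 16.1%. The print does not match the count, so both are carried.
- Exact 95% interval for 9/62: 6.9% to 25.8%.
- Expected number, n × p: 15 × 0.145 = 2.2 and 24 × 0.145 = 3.5. At 16%: 15 × 0.16 = 2.4 and 24 × 0.16 = 3.8.
- Chance of at least one, 1 − (1 − p)^n: at 9/62, 90% for n = 15 and 98% for n = 24; at 16%, 93% and 98%.
- Over the interval: 15 × 0.069 = 1.0 to 15 × 0.258 = 3.9 events in 15 patients; 24 × 0.069 = 1.7 to 24 × 0.258 = 6.2 in 24.

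With so few events expected, leaving out one or two would remove a large share of what the committee could see.

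**The case against.** The best defence is that the exclusion is narrow. It applies in general, only to events that are clearly progression, and only if they are not due to treatment. An event that cannot be told apart from toxicity is not clearly progression, and the reasonable-possibility standard in 11.1 would arguably make it related. The 11.0 rule concerns recording on the case report form and can stand beside an exception to SAE reporting. Section 10.0 makes the PI ultimately responsible for safety and sets the committee's remit by grade, without an attribution filter.

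Much of this stands. A reader might infer that such events will escape the DSMC. The text supports only that they can: a careful investigator applying the word clearly would report an ambiguous deficit. Nor is the DSMC the only safeguard, given the PI's duty and the opening sentence of 11.2.

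Two things remain. Read as a rule with an exception, 11.2 still keeps index-level decline attributed to progression out of SAE reporting. And a remit defined by grade does not bring an event to the committee if no report is sent.

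**Conclusion.** The point holds as a drafting conflict with a safety consequence. Section 11.2 leaves it open whether a serious neurologic event at the treated level, attributed to progression, goes to the board, and its attribution test omits the intervention. The event would not be lost from the trial's data, but it could be missing from the SAE reports and from the treatment-related endpoint.

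Its size cannot be measured from the documents. The 2.2 to 2.4 events in 15 patients, or 3.5 to 3.8 in 24, might be taken for the number withheld. They are not: they count neurologic progressions of any cause, and no withholding rate can be derived. They also assume that a rate seen with single doses of 14-20 Gy applies to a trial with a first fraction of 8-24 Gy and its own cord limits.

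A reader might also infer from the cited series that most such decline is toxicity. Causes are given for only 3 of the 9 patients (2 necrosis, 1 tumour progression), and the text does not say what tissue was necrotic. The series shows mixed causes and no more. Nor do the documents show that waiting between fractions causes decline.

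**What to change.** Three edits to Section 11.2:

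1. Reconcile the sentences, stating whether the progression exclusion is an exception to the any-SAE duty and that recording under 11.0 applies in every case.
2. Replace study drug(s) with study treatment or intervention in the exclusion and in the death exemption, to match 11.1.
3. Add: *Neurologic deterioration, surgery or death attributed to the index spine level that meets the Section 11.1 seriousness criteria or is grade 3 or higher is reported to the DSMC whatever its attributed cause. The progression exclusion applies only to events away from the treated level.*

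The threshold in the third edit matters. Without it, mild worsening would become reportable as serious, against the definitions in 11.1. The edits change no treatment or assessment. The cost is a few extra reports. The exact number cannot be derived: some of these events would be reported under the present text, and index-level deaths or operations could add others.

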## 13.0 APPENDICES

### 13.1 Appendix A – Eligibility Checklist

#### Inclusion Criteria

Must be answered **YES** for eligibility

1. Does the patient have pathologically proven malignancy? **Yes / No**
2. Does the patient have demonstrated metastatic epidural cord compression on diagnostic imaging? **Yes / No**
3. Has the patient been evaluated by neurosurgery or orthopedic surgery and is not proceeding? **Yes / No**
4. Has the patient had an appropriate pre-treatment work-up, including complete history, physical examination and neurologic evaluation? **Yes / No**
5. Does the patient have ECOG Performance Status 0-2? **Yes / No**
6. Is the patient at least 18 years old? **Yes / No**
7. Is either of the following true?:
  - The patient is not a woman of childbearing potential.
  - The patient has undergone negative serum or urine pregnancy test within 72 hours prior to the start of study therapy, agrees to utilize an adequate method of contraception throughout treatment and for at least 4 weeks after study therapy is completed, and has been advised of the importance of avoiding pregnancy during trial participation and the potential risks of an unintentional pregnancy.**Yes / No**
8. Has the patient signed study-specific informed consent? **Yes / No**

## Exclusion Criteria

Must be answered **NO** for eligibility

1. Has the patient had prior radiotherapy to the area in question which would exceed published constraints if enrolled?

**Yes / No**

2. Does the patient have spinal instability as indicated by imaging or physical exam?

**Yes / No**

3. Does the patient have a radiosensitive histology including myeloma or lymphoma?

**Yes / No**

4. Is the patient pregnant or breastfeeding?

**Yes / No**

## 13.2 Appendix B – Common Toxicity Criteria

### NCI CTCAE Version 4.0

Toxicity will be scored using NCI CTC Version 4.0 for toxicity and adverse event reporting. A copy of the NCI CTC Version 4.0 can be downloaded from the CTEP homepage: (<http://ctep.info.nih.gov>). All appropriate treatment areas have access to a copy of the CTC Version 4.0

### 13.3 Appendix C – ECOG Performance Status

Performance Status	Definition
0	No symptoms; normal activity level
1	Symptomatic, but able to carry out normal daily activities
2	Symptomatic; in bed less than half of the day; needs some assistance with daily activities
3	Symptomatic; in bed more than half of the day
4	Bedridden

## 13.4 Appendix D – Neurologic and Functional Assessment

### Neurologic Assessment (adapted from RTOG 0631, Appendix IV)

Symptoms:

Level	Tenderness	Radiculopathy
Cervical Spine		
Thoracic Spine		
Lumbar Spine		
Sacrum		

Strength (MRC grade):

Arm	Level	L	R	Leg	Level	L	R
Deltoid	C5/6			Iliopsoas			
Bicep	C5/6			Quadriceps			
Tricep	C6/7/8			Hamstrings			
Digits	C7/8/T1			Ant Tibialis			
Interossei	C8/T1			Gastroc			

Sensation:

	Arm		Trunk		Leg	
	L	R	L	R	L	R
Normal						
Decreased						

Urinary Incontinence:

Present: \_\_\_\_\_ Absent: \_\_\_\_\_

Sphincter Tone:

Normal: \_\_\_\_\_ Decreased: \_\_\_\_\_ Absent: \_\_\_\_\_

Functional Assessment ((adapted from ICORG phase III trial, ASTRO 2014))

Mobility Score	
I	Ambulatory without aid
II	Ambulatory with aid
III	Not Ambulatory
IV	Paraplegia
